**Clinical Serological Testing:** Tests with FDA-EUA will be used to assess the presence of IgG antibodies to SARS-CoV-2 (Table 1) every 6 months. Our current Abbott Architect assay qualitatively assesses IgG binding to the SARS-CoV-2 nucleocapsid (NP) protein and we intend to offer the Architect anti-spike (S) semi-quantitative assay when it is granted EUA (expected shortly). Serum will be collected upon enrollment and then every 6 months for the duration of the study period. Assuming 70% study enrollment, this will result in 1,680 staff and 1,330 student serological tests.

[figure not shown]
**Reporting and Result Handling:** The ordering provider ([name]) at the MCC and nursing staff will receive test results. Positive results will be reported to public health agencies via standard clinical protocols. Both molecular and serological *clinical* results will be qualitative (Positive, Negative, Inconclusive). Upon the communication of a positive molecular test result, students and staff will be referred to their primary care providers (PCPs) or urgent care if lacking a PCP. Enrolled study subjects who have been in close proximity to the positive individual will be immediately PCR tested. Unenrolled, exposed individuals will be offered study enrollment or else referred to their PCP/urgent care for testing. RT-PCR positive students will be re-tested every two weeks to assess viral load kinetics.

**Research Serological Testing:** Modeling requires continuous, quantitative data to estimate antibody persistence, and as a correlate of immunity. We will test 200 subjects every 4 weeks for up to 36 months using a multiplex research assay that simultaneously measures IgG levels against the spike (S) and nucleocapsid (N) proteins of SARS-CoV-2 and human seasonal strains (OC43, HKU1, NL63, 229E); we will also measure antibodies directed against the receptor binding domain (RBD) of the S protein. This assay provides absolute measures of serum IgG (ng/ml), and is currently in use in several NIH funded studies (see Fig 1). We are also adding emerging SARS-CoV-2 variants (e.g. UK, South African). Samples will be collected by fingerstick and volumetric micro-sampling (VAMS) to collect 40 $\mu$ l of capillary blood. A topical anesthetic cream can be used prior to collection. Samples will be analyzed by batch in [name] lab.

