### Scientific Goal 2: Serological Testing and Modeling

The dynamics of the immune response to SARS-CoV-2 are as yet unknown in children with IDD, a population with prevalent immunological dysfunction, who may show different COVID-related immunological profiles and latencies to those of the general population. Here, we longitudinally follow those with IDD identified as antibody-positive, from either infection or vaccination, to quantify the timing of reductions in IgG and neutralizing antibody levels. We will use a combination of the SARS-CoV-2 clinical serological assay (described above), and a research multiplex assay for anti-spike and nucleocapsid protein IgG and receptor binding domain (RBS) antibodies, against SARS CoV-2 (including emerging virus variants), and a panel of commonly circulating human coronaviruses. *This will provide serological data uniquely focused on the IDD population with clear implications for public health immunity strategies.*

**Experimental Approach.** IgG responses to individual SARS-CoV-2 antigens (S, NP, RBD) in enrolled students and staff will be measured initially by clinical testing and fingerstick at baseline, and then every four weeks by fingerstick for up to 36 months. Any large increase in anti-SARS-CoV-2 levels will be confirmed by clinical serology. Dynamics of anti-SARS-CoV-2 IgG will be assessed by fitting the anti-S, NP and RBD quantitative results to a modified power law model that accounts for long-term antibody persistence:  $f(t) = k + \log [(1 - \lambda)(c + t)^{-\alpha} + \lambda]$ , where  $k$  is the peak log IgG level,  $\alpha$  is the decay rate,  $c$  is a constant, and  $\lambda$  is the steady-state long-term IgG level. We will fit the model using a mixed effects

**Figure 1 – Serological Testing.** (A) Clinical analysis of persistence of anti-S, anti-NP, and anti-RBD binding IgG and PCR results from the URMC Clinical Laboratory. Note the early decline of anti-NP IgG. (B) Multiplex testing for IgG directed against S proteins for common circulating coronaviruses, including SARS-CoV-2 (SARS2), and prior SARS-CoV-1 and MERS (Middle East Respiratory Virus)

method, where  $k$  and  $\alpha$  are subject specific random effects drawn from a bivariate normal distribution. This will allow comparison of decay rates ( $\alpha$ ) and steady state anti-SARS-CoV-2 IgG levels ( $\lambda$ ) across subjects.

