**Contingency Plans:** During COVID, MCC has had to respond to immediate changes in requirements from DOH and the NYS Governor. The process to "pivot" will be replicated, as it has worked well within the organization structure. Upon notification of a change, this will be broadly communicated to the project team, with same day conference established to evaluate and implement required changes. We anticipate during the course of this study that vaccinations will be approved for children under 16. This opportunity will be incorporated into educational initiatives, and will be recorded for study participants. Our scientific goals as outlined herein have built in contingencies around the expected introduction of vaccines in this population. We will also work with NIH program to revise the research and testing program in response to major changes in policy. The modeling goal described above is specifically designed to react to changing infection/vaccination landscapes.

**Community Partnerships and Engagement:** Our goal is to enroll 70% of eligible students and staff at MCC. This enrollment projection is based on past local experience of [name] and the MCC leadership, and the high motivation level of MCC parents/guardians and staff. To increase participant engagement and interest in the project we will modify our proposed student recruitment and retention approaches based on key input and feedback from MCC leaders and a convenience sample of parents/guardians (9, 10). Our approach will start with an Introduction Phase followed by an Engagement phase, concluding with a Consent phase that includes baseline (and follow-up) surveys to characterize the participants, their households and community of residence. The UR Clinical and Translational Science Institute (directed by MPI [name]) will assist, and has extensive experience in community engagement, recruitment and retention of special populations. The IDDRC Human Phenotyping and Recruitment (HPR) Core will also be leveraged for their expertise including recruiter training and retention strategies.

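### Fingerstick IgG samples are assayed in batches, but the decay model has no run term and no batch rule or bridging control is given; with calendar-ordered runs, run shifts enter the decay rate and its interval is too narrow.

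*Protocol*

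**What the plan says.** Protocol 1.4, Goal 1 (Research Serological Testing): "We will test 200 subjects every 4 weeks for up to 36 months using a multiplex research assay". Results are reported as absolute concentrations in ng/ml. The same paragraph says "Samples will be analyzed by batch" and, of the panel, "We are also adding emerging SARS-CoV-2 variants". Batch size, the interval between runs, batch make-up, control samples and between-run error are not stated.

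Protocol 1.4, Goal 2 (Experimental Approach): IgG to the separate antigens "in enrolled students and staff will be measured initially by clinical testing and fingerstick at baseline", then 4-weekly. The data are fitted to a "modified power law model that accounts for long-term antibody persistence", f(t) = k + log[(1 − λ)(c + t)^(−α) + λ], in which k and α "are subject specific random effects drawn from a bivariate normal distribution". No other random effect is written. The stated use is to compare decay rates and steady-state levels across subjects. The Goal 2 summary in 1.3 asks whether immunity in children with IDD wanes faster than in the population at large.

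Protocol 1.4, Contingency Plans: "We anticipate during the course of this study that vaccinations will be approved for children under 16".

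The SAP says that the time course of the immune response will be evaluated. It gives no model and no handling of runs.

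**The concern.** A run that reads high or low moves every sample in it together. In a model with only subject effects and independent residuals, the fit treats that common movement as part of each person's curve. If runs are filled in calendar order, people with similar exposure dates pass through the same runs at similar times since exposure. The run shifts then tilt all their slopes in the same direction. The between-subject spread, on which the standard error rests, hardly registers this.

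Durability of the antibody response in children with IDD is the Goal 2 question. An interval that is too narrow could support a firm statement about waning that the assay cannot bear. Reporting in ng/ml implies calibration, but the documents do not say what error is left between runs.

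**Working it through.** The plan gives no sample size, standard error or assay precision for the decay analysis, so there is no figure of its own to reproduce.

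**Inputs from the protocol.** 200 subjects; 4-weekly samples for up to 36 months, which is 156/4 = 39 visits after baseline; power-law decay with random k and α.

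**Assumptions.** 100 students and 100 staff; mean α 1, SD of α 0.3; residual SD 0.3 on the natural-log scale; λ = 0, c = 1; run shifts N(0, s²) with s = 0.05, 0.10 or 0.20 (about 5, 10, 20%); quarterly calendar-ordered runs; no true group difference. Each person's slope is taken on log time, and group means are compared by a t-test. Follow-up is either 9 samples or the planned 39.

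**Mechanism by hand (9 samples, one group, all starting together).** With x = ln 1, …, ln 9, the mean of x is 1.422 and Sxx = 4.139.

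- Model SE of the mean slope: √[(0.3² + 0.3²/4.139)/100] = √(0.1117/100) = 0.0334.
- Centred x summed within the three runs: −2.476, 0.520, 1.955. Root sum of squares = √10.22 = 3.197.
- Extra SD from run shifts: s × 3.197/4.139 = 0.77s. There is no division by the number of subjects.
- At s = 0.10 the true SD is √(0.0334² + 0.077²) = 0.084, against a reported 0.033. Coverage is 2Φ(1.96 × 0.0334/0.084) − 1 = 0.56.

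**Simulation with staggered starts.** Staff clocks start in months 0–3. Students start in the same months or, in the lagged case, in months 6–10.

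| Quantity | Samples | s = 5% | 10% | 20% |
|---|---|---|---|---|
| 95% CI coverage, one group's mean decay rate | 9 | 0.86 | 0.71 | 0.40 |
| Same | 39 | 0.94 | 0.85 | 0.66 |
| Rejection, nominal 5% student-staff test, lagged starts | 9 | 16% | 39% | 66% |
| Same | 39 | 6% | 12% | 25% |
| Rejection, same start months, shared runs | 9 or 39 | near 5% | near 5% | near 5% |

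Repeat runs moved the table entries by up to about 0.05. Staggering spreads people over runs, so 0.71 is milder than the hand result of 0.56.

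**Sensitivity.**

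- Monthly runs, lagged starts: rejection is about 9%, 20% and 46% with 9 samples, and 5%, 8% and 12% with 39.
- Wide overlapping starts (staff months 0–12, students 4–16), s = 10%, quarterly: 9% with 9 samples, 6% with 39.
- A variant with 40 visits and SD of α 0.2, groups in separate runs: coverage of the difference 0.89, 0.73 and 0.47.
- That variant with a lag of about 6 months: 0.94, 0.84 and 0.64. With λ = 0.05 it is 0.53 at s = 10% and 0.32 at 20%.
- Whole series in one run: coverage of the mean decay rate 0.94–0.95.

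**With a run random effect** (the 40-visit variant, s = 10 and 20%, variance components taken as known): coverage of the mean decay rate returns to 0.94–0.97. Coverage of the lagged difference rises from 0.86 and 0.65 to 0.96 and 0.96.

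**The case against.** A reader might infer that batch analysis without a run term makes the student-staff interval too narrow in general, so that a false finding of faster or slower waning is likely. The documents do not support that.

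- **Cancellation.** With shared runs and similar exposure timing, the shifts cancel in the difference.
- **Run order.** Calendar-ordered batches are an inference. The protocol does not say how batches are made up, and running each participant's series together would remove the problem.
- **Timing.** The exposure lag is also inferred. The remark on vaccine approval concerns children under 16 only, and 8% of students are 18–21. Goal 2 follows antibody from infection as well as vaccination, and infection dates need not wait for approval.
- **Comparator.** No student-staff test is written. The text speaks of the population at large and of comparison across subjects.
- **Size.** No between-run SD is given. The larger rejection rates rest on 9 samples per person, and the full schedule cuts them sharply. Adding variant antigens does not by itself show that the S, NP or RBD readings move.

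All of this stands, and it limits the student-staff part to a conditional risk. It does not answer the first part: with calendar-ordered runs a single group's decay rate is affected even when the groups' timing is identical, and nothing in the plan rules that layout out. A lag for vaccination is plausible, since 20 + 28 + 25 = 73% of students are 14 or younger and staff are adults. Staff are also the only non-IDD group measured on this assay. Against an external comparator, run error would not be shared and could not be expected to cancel.

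**Conclusion.** The point holds in conditional form. The written model omits a source of error that batch analysis can introduce, and the plan has no bridging control or allocation rule that would contain it. If runs follow calendar order, the interval for a group's decay rate is too narrow: slightly so at a run SD of 5% with full follow-up (coverage about 0.94), badly so at 20% with short follow-up (about 0.40).

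A student-staff contrast is at risk only if exposure dates differ by group or the groups are run separately. In the lagged quarterly case the false-positive rate runs from about 6% to 66% across the run SDs and follow-up lengths tried. Elsewhere it stays near 5%. A general claim that this contrast is wrong, or that a false result is likely, is not supported.

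The run SD, run interval, variance components and start dates are all assumptions. The change is worth making because allocation and controls must be settled before samples are run; runs without a common reference cannot be fully repaired afterwards.

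**What to change.** 1. Add an assay-run random effect to the Goal 2 model, for each antigen: y_ij = k_i + log[(1 − λ)(c + t_ij)^(−α_i) + λ] + b_r(ij) + e_ij, with b_r ~ N(0, σ_b²) for the run r in which the sample was assayed. State this in the SAP and report σ_b.
2. Put the same control samples in every run, and carry them across any change of antigen panel, so that run shifts can be estimated apart from decay.
3. Mix student and staff samples in each run. This deals with separate runs; it does not remove the effect of a lag, for which items 1 and 2 are needed.
4. Where stored samples allow, run each participant's series together. A run shift then moves the level k and leaves the slope alone.
5. Write down the allocation rule, and record run and lot with every result.

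Cost: a few wells per run, a loading rule for the laboratory and one model term. Intervals will be somewhat wider. Holding a full series for one run delays those results, so items 1 to 3 should apply wherever the iterative modeling needs data sooner.

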### Scientific Goal 2: Serological Testing and Modeling

The dynamics of the immune response to SARS-CoV-2 are as yet unknown in children with IDD, a population with prevalent immunological dysfunction, who may show different COVID-related immunological profiles and latencies to those of the general population. Here, we longitudinally follow those with IDD identified as antibody-positive, from either infection or vaccination, to quantify the timing of reductions in IgG and neutralizing antibody levels. We will use a combination of the SARS-CoV-2 clinical serological assay (described above), and a research multiplex assay for anti-spike and nucleocapsid protein IgG and receptor binding domain (RBS) antibodies, against SARS CoV-2 (including emerging virus variants), and a panel of commonly circulating human coronaviruses. *This will provide serological data uniquely focused on the IDD population with clear implications for public health immunity strategies.*

**Experimental Approach.** IgG responses to individual SARS-CoV-2 antigens (S, NP, RBD) in enrolled students and staff will be measured initially by clinical testing and fingerstick at baseline, and then every four weeks by fingerstick for up to 36 months. Any large increase in anti-SARS-CoV-2 levels will be confirmed by clinical serology. Dynamics of anti-SARS-CoV-2 IgG will be assessed by fitting the anti-S, NP and RBD quantitative results to a modified power law model that accounts for long-term antibody persistence:  $f(t) = k + \log [(1 - \lambda)(c + t)^{-\alpha} + \lambda]$ , where  $k$  is the peak log IgG level,  $\alpha$  is the decay rate,  $c$  is a constant, and  $\lambda$  is the steady-state long-term IgG level. We will fit the model using a mixed effects

**Figure 1 – Serological Testing.** (A) Clinical analysis of persistence of anti-S, anti-NP, and anti-RBD binding IgG and PCR results from the URMC Clinical Laboratory. Note the early decline of anti-NP IgG. (B) Multiplex testing for IgG directed against S proteins for common circulating coronaviruses, including SARS-CoV-2 (SARS2), and prior SARS-CoV-1 and MERS (Middle East Respiratory Virus)

method, where  $k$  and  $\alpha$  are subject specific random effects drawn from a bivariate normal distribution. This will allow comparison of decay rates ( $\alpha$ ) and steady state anti-SARS-CoV-2 IgG levels ( $\lambda$ ) across subjects.

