#### **1.4 CENTRAL AIMS**

**Scientific Goal 1: Establish a molecular testing program to monitor and identify COVID-19 infections within a school community of individuals with IDD**

**Overview and rationale:** This program will focus on the students (n=450) and staff (n=500) of the MCC, who collectively form a community that is highly representative of other IDD school communities across the nation. We will establish testing across this difficult-to-test population, using a tailored and flexible approach to foster test uptake and to prevent and/or mitigate COVID-19 outbreaks.

**Establish a clinical molecular and serological COVID-19 testing program for the Mary Cariola Center:** The dynamics of viral spread are unknown in a school serving individuals with IDD such as the MCC. Questions to be answered with *molecular* testing include: What is the incidence of asymptomatic COVID-19 infection, and how is this affected by rising vaccination rates? How do activities within the school alter risk? *Serological* testing will assess baseline prevalence of prior infection (anti-NP IgG), and changes over time, in response to infection (anti-NP IgG+) and vaccination (anti-S IgG+, anti-NP IgG-).

**Molecular Testing:** RT-PCR tests for SARS-CoV-2 with FDA EUA will deliver highly sensitive and specific clinical-grade results. Respiratory samples will be obtained by mid-turbinate or nasal swabs, collected in a dedicated area with proper ventilation and PPE (see Mobile Unit testing plan below), and delivered to the URMC Central Laboratory for testing in a CLIA environment with 24-72h turnaround times. The testing plan includes two groups: those tested as part of scheduled surveillance and those tested for symptoms or exposure.

**Surveillance Screening and Exposure/Symptomatic Testing:** Participants will be tested every 5-14 days to increase likelihood of detecting infected but asymptomatic individuals. Enrolled students and staff who report symptoms in the on-site screening will be tested on-site. Symptomatic individuals will be tested separately from asymptomatic participants every 3 days for up to 10 days. *Reported* test results will be qualitative, although Ct (cycle threshold) values will also be captured for modeling purposes.

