## 2. CHARACTERISTICS OF THE RESEARCH POPULATION

### 2.1 Subject Characteristics

All staff and students at Mary Cariola Center (MCC) are eligible for this study

**a) Number of Subjects** – There are 500 on-site staff and 450 students. Up to 950 people may enroll, although we expect around 70% enrollment

**b) Gender and age of subjects** – Among MCC **employees**, approximately 75% are female. We expect at least 50% to consent to testing and another 30% to complete the baseline survey.

**Among students under age 18**, approximately 30% are female, consistent with the national IDD population. We expect 70% to enroll. Unless our enrollment trends show otherwise we do not anticipate any unique messaging or additional outreach to achieve our enrollment target. There are also Mary Cariola students age 18-21 approximately 30% female.

**There are no exclusions by age** however we are limited by the ages of those attending or residing in MCC and the age range of employees.

**MCC students** are included in this study as the main participants as the study seeks to understand testing and transmission patterns among individuals with IDD in school and residential settings including modeling. Most of the students in the school setting are under age 18; The youngest student is age 3. There are also about 60 students at the school between the ages of 18-21. Approximately one third of these students have legally authorized representatives (guardians).

Age distribution of students is:

3-5	20%
6-10	28%
11-14	25%
15-17	19%
18-21	8%

We will track early enrollment to determine if rates are lower than expected or if there are under-represented age groups (based on the age distribution of MCC students). This will warrant revising of recruitment strategies and tactics within the research team and the CAB.

**MCC Staff** range in age from 18 to 75.

STUDY #: 5294

Version Date: 04/17/2023

Page 9 of 27

Efforts to enroll employees will be informed by the CAB. We will track early enrollment to determine if rates are lower than expected or if there are under-represented age groups. Lower than anticipated enrollment will warrant revising of recruitment strategies and tactics within the research team and informed by the CAB.

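### The Goal 2 antibody decay model does not separate infection from vaccination, so a difference in waning between students and a comparator can reflect the source mix rather than IDD

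*Protocol*

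**What the plan says.** Goal 2 states whom it follows: "we longitudinally follow those with IDD identified as antibody-positive, from either infection or vaccination". Under Experimental Approach, IgG to S, NP and RBD "in enrolled students and staff will be measured initially by clinical testing and fingerstick at baseline", then every four weeks for up to 36 months. On the analysis it says: "Dynamics of anti-SARS-CoV-2 IgG will be assessed by fitting the anti-S, NP and RBD quantitative results to a modified power law model", namely f(t) = k + log[(1 − λ)(c + t)^(−α) + λ]. Here k and α are subject-specific random effects from a single bivariate normal distribution, and α and λ are then compared across subjects. No covariate, stratum or time origin is given.

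The purpose is stated in section 1.3, under Serological Testing: to learn whether immunity in children with IDD wanes faster than in the population at large.

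Other parts of the protocol bear on the source of antibody:

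- Section 1.4, Goal 1, describes serological change "in response to infection (anti-NP IgG+) and vaccination (anti-S IgG+, anti-NP IgG", with a minus sign after the last anti-NP. Vaccination alone is therefore taken to give no anti-NP response.
- Contingency Plans (under Goal 3): "We anticipate during the course of this study that vaccinations will be approved for children under 16". Vaccination will be recorded for participants.
- Section 2.1 gives student ages: 20% are 3-5, 28% are 6-10 and 25% are 11-14.
- Section 4.1 says unvaccinated staff must be tested weekly under a vaccine mandate, and that enrolment in the study is one way to comply.

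The SAP says only that the time course of the immune response to vaccination and infection will be evaluated. It gives no model.

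**The concern.** The decay model is written out in full, and source of antibody is not in it. Antibody raised by infection and antibody raised by vaccine need not decline alike. For anti-NP, on the protocol's own account, a vaccine-only person has nothing to decline: the series is flat background and gives an exponent near zero.

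There is reason to expect the mix to differ by group. At least 20 + 28 + 25 = 73% of students were below the age at which vaccine was available when that text was written, so their early antibody could come only from infection. Staff are adults and could have either source. Group and source would then be confounded, and a group difference in α could be reported as accelerated or slowed waning in IDD when waning is the same. That is the central serological question, and Goal 2 claims public health implications for its answer.

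**Working it through.** **No figure to reproduce.** The documents give no sample size, SD, effect size or error rate for the waning comparison. Everything numerical below rests on assumptions.

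**1. Does any text supply a source term?** Vaccination is recorded (Contingency Plans). Rates of prior infection and vaccination feed the network models (Goal 3). Vaccinated and unvaccinated people are compared for memory B-cell recall (section 4.1). None of these reaches the decay model, and neither does the SAP.

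**2. Size of the bias.** Let p be the infection-derived share in each group. With no true IDD effect,

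apparent difference in mean α = (p_students − p_comparator) × (α_infection − α_vaccine).

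It is zero if either bracket is zero.

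**3. Anti-NP, if vaccine-only people are fitted.** Assumptions: 100 students and 100 staff; monthly samples for 24 months; in infected people α has mean 1.0 and SD 0.3, λ = 0.02, c = 1; vaccine-only people flat; residual SD 0.15 log10. Each person's slope on log10(1 + t) is estimated and group means are compared by a Welch test at 5%. The floor λ pulls the mean fitted exponent in infected people down to 0.83. Group means are then 0.83 × p:

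| Infection share, students / staff | Mean fitted exponents | False rejection |
|---|---|---|
| 80% / 30% | 0.66 vs 0.25 | 100% |
| 60% / 30% | 0.50 vs 0.25 | 98-99% |
| 50% / 40% | 0.42 vs 0.33 | 25-29% |
| 30% / 30% | 0.25 vs 0.25 | 4-6% |
| Infected people only | 0.83 vs 0.83 | 4-7% |

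Ranges are over repeat runs. A 50/150 split at 60%/30% gives 93-94%.

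**4. Anti-S or anti-RBD, where decay by source is unknown.** Same set-up, with an assumed α for each source:

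| Infection share | α by source | Nominal difference | False rejection |
|---|---|---|---|
| 80% / 30% | 1.2 and 0.8, either way round | 0.5 × 0.4 = 0.20 | 94-96% |
| 80% / 30% | 1.1 and 0.9 | 0.5 × 0.2 = 0.10 | 52-53% |
| 60% / 40% | 1.2 and 0.8 | 0.2 × 0.4 = 0.08 | 28-29% |
| 60% / 40% | 1.1 and 0.9 | 0.2 × 0.2 = 0.04 | 12-16% |
| 50% / 40% | 1.05 and 0.95 | 0.1 × 0.1 = 0.01 | about 6% |

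A wider closed-form grid (mix differences 0.1 to 0.7, α differences 0.1 to 0.5, SD 0.3) gives apparent effects of 0.01 to 0.35. The chance of declaring one in the direction of the bias is 4% to about 100%.

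**5. Does a source term remove it?** A separate simulation used subject-level α with SD 0.3, estimation error SD 0.1, 100 per group and 4,000 runs, at a 70%/30% mix:

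| α infection / vaccine | Without source term | With source term |
|---|---|---|
| 1.0 / 0.7 | difference +0.12, 69% | 0.00, 4.6% |
| 0.7 / 1.0 | difference −0.12, 70% | 0.00, 4.4% |
| 1.0 / 0 (NP-like) | difference +0.40, 99.8% | 0.00, 4.5% |

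**6. A caution on the anti-NP entry rule.** Suppose infected people are identified by being anti-NP positive at entry, six months after infection, with a cutoff at 10% of peak. Entry requires 0.98 × 7^(−α) + 0.02 > 0.10, so α < ln(0.98/0.08)/ln 7 = 1.29. The mean of a normal (1.0, SD 0.3) cut off above at 1.29 is 0.91. That rule keeps slow decayers.

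**The case against.** Several points on the other side are sound.

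- A reader might infer that the protocol states it will fit anti-NP decay in vaccine-only people. It does not. Goal 2 speaks of responses to individual antigens in people who are antibody-positive, and an analyst could take that to mean NP-positive people for the NP fit. The near-100% anti-NP figures apply only if vaccine-only people are fitted. What stands is that no rule excludes them.
- A reader might infer a planned student-staff test at 5%. There is none. Section 1.3 names the population at large, Goal 2 says only that subjects are compared, and the SAP is descriptive. Students versus staff is inferred because staff are the only non-IDD data in the study. An outside comparator would raise the same question of mix.
- The 80%/30% mix is assumed. Follow-up of up to 36 months may extend past vaccine approval for younger students. Using enrolment to meet the weekly testing rule could enrich enrolled staff for unvaccinated people and narrow the gap. The simulations also leave out people both infected and vaccinated.
- For anti-S and anti-RBD, the documents give no decay rates by source, so a false difference is possible, not assured, and its direction is unknown.
- Sex also differs (staff about 75% female; among students under 18, "approximately 30% are female, consistent with the national IDD population"). A reader might infer that sex must be in the model. Nothing in the documents says decay differs by sex, so that does not follow.

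The confounding route remains: the one model that is written down has no means of separating source from group.

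**Conclusion.** The concern holds as a possible confounding, not as a demonstrated error. As written, the Goal 2 model can attribute to IDD a difference in α that comes from the mix of infection and vaccination. For anti-NP this follows if vaccine-only people enter the fit and the mix differs. For anti-S and anti-RBD it also needs decay to differ by source. Under the assumptions shown, the false-difference rate runs from about 5% to nearly 100%, so no single figure should be quoted as the expected error. The simulations are two-stage simplifications of the nonlinear mixed model.

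This should be fixed before the serology is analysed. It does not threaten the data: PCR results, anti-NP and vaccination status are already collected, and the SAP puts its primary focus on spread of infection.

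**What to change.** Amend the Goal 2 text and carry it into the SAP:

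1. Classify each person-period as infection only, vaccination only or both, from PCR, serial anti-NP and recorded vaccination.
2. Fit anti-NP decay only in people with evidence of infection (PCR-positive, or NP seroconversion during follow-up), with t measured from the infection. Analyse those known only by anti-NP positivity at entry separately or as a sensitivity analysis, because that rule selects slow decayers.
3. For anti-S and anti-RBD, add source as a fixed effect on k and α, restart t at a new vaccination or reinfection, and compare groups within source.
4. Name the comparator, and state that age remains confounded with IDD in any student-staff contrast. A source term does not remove that.

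A sex covariate is not required.

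The cost is wording only, with no new data collection. The price is smaller strata and wider intervals. Quantitative serology covers 200 people with no stated student-staff split, so some strata may be too small for a useful comparison; the plan should say that those will be reported descriptively.
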